4.2 Exclusion Criteria

All candidates meeting any of the following exclusion criteria at baseline will be excluded from study participation: 1) Diagnosis of dementia as determined by the Dementia Screening Questionnaire for Individuals with Intellectual (DSQIID). 2) Unable to participate in MVPA. 3) Pregnancy during the previous 6 mos., currently lactating or planned pregnancy in the following 12 mos. Participants who become pregnant will be removed from the study and referred to appropriate agencies for consultation. 4) Serious medical risk, e.g., cancer, recent heart attack, stroke, angioplasty as determined by the PCP. 5) Unwilling to be randomized. 6) Participation in a regular exercise program, i.e. ≥ 20 min/d ≥ 3 d/wk. 7) Unable to walk unassisted.

4.3 Study Enrollment Procedures

Project staff will contact local community agencies serving adults with DS, case managers, and CDDOs by mail/email, provide presentations at CDDO meetings, and text for CDDO newsletters describing the project. Interested parents/guardians, caregivers, or adults with DS will be asked to contact the study coordinator via email, our website (www.ebl.ku.edu), or a dedicated toll-free study phone number that will be included in all recruitment materials. The study coordinator will contact the interested individuals by phone to answer questions and conduct an initial eligibility screen. Zoom calls will be scheduled with those remaining interested, and potentially eligible, to obtain informed consent (participants or guardian and caregivers) and assent (participant) and determine final eligibility based on the DSQIDD scores. Project staff will send a form (fax/email) to the potential participant's PCP which describes the study and requests clearance for participation. Participants found to be ineligible will be provided with written materials describing available resources for increasing physical activity. Project staff will track ineligibility and non-participants of eligible candidates using a REDCAP database. Participants will be stratified by sex and then sequentially randomized by the study statistician with 2:2:1 allocation to the RL, RH, and UC arms.

5 STUDY INTERVENTIONS

Randomization Cohorts of ~10-20 participants will be recruited and computer randomized. Participants will be stratified by sex and age (18-30 or >30) and then sequentially randomized by the study statistician with 2:2:1 allocation to the RL, RH, and UC arms. This randomization scheme was selected to include more participants in the group video conferencing arms which, if successful, will be included in a later stage trial examining the effectiveness of increased MVPA using the video conferencing approach on cognitive function and brain health in adults with DS. Intervention assignments will be concealed in envelopes and delivered to the study coordinator.

Caregiver role. We will recruit either a parent/guardian or residential support staff, to serve as a study partner for each participant. Study partners will be allowed to assist multiple adults, provided all adults are in the same intervention group. Study partners will be asked to attend all individual support/education sessions, and to support, encourage, and assist participants in complying with the study protocol, such as reminding them to attend the group exercise sessions (RL and RH only), individual support session (all groups) providing opportunities for increased MVPA, and assisting with self-monitoring of MVPA.

MVPA recommendations. We will target 150 min/wk. of MVPA (≥ 3 METs) for all groups as recommended for all adults by the American College of Sports Medicine ¹ and the U.S. Department of Health and Human Services ². MVPA recommendations will progress from 60 min/wk. (3 d/wk., 20 min./d) to 150 min./wk. (5 d/wk., 30 min./d) at the beginning of mo. 4, and remain at 150 min./wk. through the end of the study. Accumulated MVPA in bouts ≥ 10 min will be permitted.

RL and RH Intervention.

Orientation. Each participant and their study partner will be asked to attend a group orientation session (~60 min.) conducted at the University of Kansas Medical center and led by their health educator. In addition to describing study requirements and distributing iPads, Fitbits, resistance bands, etc., this meeting is designed to establish rapport between the health educator and participants, and between participants themselves, prior to initiating the group video conference sessions. The health educator will describe and demonstrate the ZoomTM software and the Fitbit and will allow time for practice and questions. Additionally, basic stretching exercises, the use of the resistance bands, and simple dance movements will be demonstrated and practiced.

Group sessions-schedule. Group exercise sessions will be scheduled between 10 a.m. and 7 p.m., 3 days/wk. for RH and 1 day/wk. for RL. This time window was selected based on the preference of participants in our 12-wk pilot trial in individuals with DS. Prompts reminding participants of upcoming sessions will be sent via the iPad. The same health educator will conduct MVPA sessions for both the RH and RL groups in each cohort to minimize health educator effects.

Group sessions-Delivery. All MVPA sessions will be conducted by a health educator experienced in working with individuals with DS and supervised by [name]. Group sessions will be delivered using an iPad tablet computer provided to all participants. The iPad will be pre-loaded with video-conferencing software (ZoomTM) which allows participation by multiple users. Participants will be provided with an iPad/HDMI adaptor, which allows video conference sessions to be displayed on a larger TV screen, if desired. Tutorials describing trouble shooting for common technical problems, e.g., internet connectivity etc., will be loaded on the iPad. Participants with technical issues during the intervention can also contact research staff by phone or email. Access to non-study related materials, e.g., web browsing, app store, etc., will be blocked on all iPads. The iPads for both groups will also be pre-loaded with the Fitbit application.

Group MVPA session-content. Each session will include a warm-up (~5 min), moderate-to-vigorous intensity aerobic and resistance exercise (~30 min.), and cool-down/stretching (~5 min.). Resistance exercise may be especially relevant, as adults with DS have reduced muscle strength compared with their typically developing peers ³. The aerobic/resistance exercises, accompanied by music, will include walking/jogging in place, dancing, imitating animal movements, vertical/horizontal jumps, squats, and Thera-Band exercises for major muscle groups. Activities will be modified for participants having difficulty with specific movements. The intensity of the initial sessions, as determined by Fitbit, will be light-to-moderate, with intensity increasing to moderate-to-vigorous at ~ 6 wks. All participants will be able to see, hear, and speak to each other during the group sessions. During each session, health educators will encourage interactions between participants in

support of their peer's efforts to increase MVPA and provide participant feedback relative to their level of weekly MVPA as assessed by the Fitbit. As the intervention progresses, participants will be asked to volunteer to create and lead the group in a brief (3-5 min) exercise bout. Participants will also be encouraged to interact with each other by providing verbal support to each other ("great job", "keep it up"), performing activities such as tossing an imaginary ball to other participants, or challenging other participants to complete a skill such as 10 hops on one leg etc. All group sessions will be video recorded.

Homework assignments. The group exercise sessions have the potential to provide 30 min./wk. of MVPA for the RL group and 90 min./wk. for the RH group. Thus, MVPA outside these sessions will be required to meet the 150 min weekly recommendations. Health educators will provide weekly challenges in the form of meeting a goal for increased steps, trying a new activity, or creating and performing their own exercise routine etc. Participants will be provided access to video recordings of all group sessions that can be followed on their own to help in meeting weekly MVPA goals across the 12 mo. trial, if desired. Recordings will be sent to Dropbox and will be accessible to participants on the iPad. We will also provide information regarding increasing physical activity, available from the National Center on Health, Physical Activity and Disability (NCHPAD) and the Special Olympic athletes home training guide. Participants will be asked to document MVPA outside group sessions using the Fitbit, rather than video recordings as used in our pilot due to poor compliance with the video recording protocol. Participants press a button on the Fitbit at the beginning and end of each MVPA session to differentiate planned MVPA from other daily activity. Activity monitoring using the Fitbit is being successfully implemented to monitor the MVPA component in our on-going trial of weight management in adults with IDD (DK114121, [name], MPI).

Education/support sessions. Bi-Weekly (2x/mo) 20-min. education/support sessions will be delivered to participants and their study partners remotely on the iPad using Zoom™. These sessions, led by the health educator, will be designed to educate and support the participant with meeting their 150 min./wk. MVPA goal. Each session will include a review of MVPA self-monitoring data, goal setting, strategies to increase and support MVPA, and discussion of a topic relevant to MVPA including: the importance of MVPA for health and function, how to include MVPA in the daily schedule, reducing barriers to MVPA, appropriate types of activity, creating a safe environment for MVPA, alternative activities for inclement weather, importance of hydration, etc. Session outlines and materials will be preloaded on the iPad where they can be accessed by participants at any time.

UC Intervention.

Orientation. Participants and their study partner will be asked to attend an orientation session (~60 min.) conducted at the University of Kansas Medical center and led by their health educator. In addition to describing study requirements and distributing iPads, Fitbits, resistance bands, etc., this meeting is designed to establish rapport between the health educator and participants. The health educator will describe and demonstrate the Zoom™ software and the Fitbit and will allow time for practice and questions. Additionally, basic stretching exercises and the use of the resistance bands will be demonstrated and practiced.

Intervention. The UC intervention will follow the traditional approach to promote increased MVPA in individuals with DS previously used by our group ⁴⁻⁶ and others ⁷⁻⁹. Participants will receive an iPad tablet loaded with information regarding increasing MVPA available from NCHPAD and the Special Olympic athletes home training guide, and will also receive resistance bands and a Fitbit for self-monitoring MVPA (described below). Bi-weekly 20-min. education/support sessions, identical to the education/support sessions provided in the RL and RH arms, described above, will be

delivered to participants and their study partners remotely on the iPad using Zoom^M. Session outlines and materials will be preloaded on the iPad where they can be accessed by the participant at any time.

MVPA-self monitoring. Participants in all 3 groups will be asked to wear a Fitbit Charge 3TM (35.5 mm x 28 mm) activity tracker on their non-dominant wrist over the duration of the 12-mo. trial. This request may appear onerous; however, wearing the Fitbit is akin to wearing a wristwatch. Real-time data from the Fitbit is automatically transferred, via the web, to cloud storage (Fitabase, Small Steps Labs LLC, San Diego, CA), thus participant burden is minimal. Immediate participant feedback via a graphic display of daily steps, minutes of sedentary time, time spent in light, moderate and vigorous PA will be available on the iPad. This data, accessible to health educators, will be used to provide motivation and feedback during the education/support sessions. Participants will be reminded to wear and charge the Fitbit during the individual support/education sessions, and will receive automatic reminder messages via the iPad using the iCal app. These procedures were used successfully in our previous trials in adults with DS^{4, 6, 10, 11}.

Health educator training/ fidelity

Training. We currently have 3 health educators with experience in delivering group exercise and individual education and support using video conferencing to groups of adults with DS. If needed, new health educators will be trained and will shadow an experienced health educator for a minimum of 3 mos. prior to delivering the intervention on their own. We will conduct weekly meetings with all health educators to discuss issues relative to intervention delivery.

Intervention fidelity. A study team member will review recordings from all scheduled group MVPA and individual support sessions. The content delivered will be compared with a checklist of scheduled activities/topics. Feedback will be provided to all health educators; those covering <80% of scheduled activities/topics will receive additional training and will be dismissed if the problem recurs.

Participant Incentives. Reinforcement systems, known as positive behavioral support programs, have been successful in promoting behavioral change in individuals with DS¹². These strategies provide modest incentives to motivate participants to meet their goals, and were successfully used in our previous trials that included adults with DS^{4, 5, 10}. Participants in all groups who complete self-monitoring of MVPA on 5 of 7 d/wk. will be allowed to choose an iTunes song which will be uploaded weekly to the participant's iPad by study staff. Additionally, to compensate for time and travel, participants will receive \$200 for completion of each of the 3 outcome assessment laboratory visits (baseline, 6, 12 mos.), and \$50 for completion of the additional two accelerometer outcome collection periods (3 and 9 mos.). As an additional incentive, participants will be allowed to keep the iPad and Fitbit on completion of the trial (12 mos.).

Blinding. The nature of this trial precludes blinding of the health educators; however, investigators, data analysts and research assistants will be blinded to condition

ASSESSMENTS

With the exception of assessment of daily MVPA by accelerometer, all outcomes will be assessed at the University of Kansas Medical Center, in Kansas City, KS. Cognitive function, cardiovascular fitness, and quality of life will be assessed at the Center for Physical Activity and Weight Management (CPAWM) and all neuroimaging outcomes will be assessed at Hoglund Brain Imaging Center (HBIC), which is located next door to the CPAWM. Our experience with similar trials suggests these assessments, which will be completed by trained staff blinded to condition, will

require ~2.5 hrs. to complete. Some assessments will only be collected on a sub-sample of participants.

Primary Outcome- MVPA.

Schedule. MVPA will be assessed at baseline, 3, 6, 9, and, 12 mos. Equipment. MVPA will be assessed using an ActiGraph (ActiGraph wGT3XBT, ActiGraph LLC, Pensacola, FL) tri-axial accelerometer (3.3 x 4.6 x 3.5 cm, wt. = 19 g., dynamic range \pm 8 g). The ActiGraph provides valid and reliable assessments of physical activity in adults ¹³⁻¹⁵, and has been widely used to describe physical activity levels in adults with DS ¹⁶⁻¹⁸. Our group has used the ActiGraph in previous trials in adults with IDD ⁴, and in typically developing adults ^{19, 20}. We have also developed a custom program for processing ActiGraph data, using protocols described subsequently. Protocol. There is a lack of consensus on the best protocols to collect, process, and score ActiGraph data ²¹⁻²⁴. Thus, our decisions regarding ActiGraph location, monitoring period, data processing, etc. were based on current practice, as described below. Participants will be asked to wear the ActiGraph on a belt over the non-dominant hip at the anterior axillary line during waking hours for 7 consecutive days, with the exception of bathing, swimming, and contact sports. A 7-day monitoring period provides a reliable estimate of MVPA ^{22, 25, 26}. The hip rather than the wrist location will be used due to the lack of comparable data, and established protocols for assessment of MVPA using wrist-worn ActiGraphs ²⁷⁻²⁹. ActiGraph distribution/reminders. Research staff will distribute and demonstrate proper placement of the ActiGraphs at laboratory visits scheduled at baseline 6, and 12 mos. ActiGraphs will be distributed by mail for the 3, 9 mo. assessments. ActiGraphs will be returned by postage paid mail following completion of all assessments. Daily reminders to comply with the ActiGraph protocol will be sent to participants' iPads each morning during the 7-day monitoring period. We have employed similar distribution and reminder protocols in previous trials ^{4, 6, 20, 30, 31}. Our current supply of ActiGraphs, plus the additional units requested in this proposal, will allow assessments to be completed on all participants in the proposed timeframe. Data collection. ActiGraphs will be initialized and downloaded using ActiLife Software version 6.13.3 or higher (ActiGraph Corp, Pensacola, FL) and set to collect in the raw data mode from all 3 axes at 60 Hz. Although the wGT3XBT collects raw data from 3 axes, results from studies assessing the benefit of 3 axes vs 1 axis (vertical) are conflicting ³²⁻³⁴. In addition, there are currently no established algorithms for using either the raw data or the vector magnitude (square root of the sum of the squares of each of the 3 axes) to estimate MVPA ^{35, 36}. The widely used cut-points for determining activity intensity in adults ³⁷ proposed for this trial use acceleration data from the ActiGraph vertical axis. However, raw data from all 3 axes will be downloaded and stored; and will be available should algorithms for processing this data become available during the course of this trial. Data processing. Accelerometer data will be processed using the protocol for adults used in the 2003-2004 and 2005-2006 cycles of NHANES ^{37, 38}. Data will be aggregated over 60-sec epochs. The following intensity cut-points will be used: sedentary (< 1.0 MET; \leq 100 counts/min), light (1.1-2.99 METs; 101-2019 counts/min.), moderate (3.0-5.99 METs; 2020-5988 counts/min) and vigorous \geq 6 METs; \geq 5999 counts/min) ^{37, 38}. Non-wear time will be defined as at least 60 consecutive minutes of zero counts, with allowance for 1-2 min. of counts between 0 and 100. Counts \geq 20,000/min will be considered spurious ³⁹. All accelerometer data processing will be completed using custom SAS/R programs developed by our team.

Cognitive Function. Working memory, processing speed, multitasking, and episodic memory will be assessed using tests selected from the widely used Cambridge Neuropsychological Test Automated Battery (CANTAB®, Cambridge Cognition, LTD, Cambridge, UK) ⁴⁰⁻⁴⁵. These standardized tests have been extensively evaluated, provide normative data, and allow for comparisons across trials. CANTAB® tests have acceptable construct ^{40, 46, 47} and concurrent validity ⁴⁷. Specifically, we will use the CANTAB®, DS Battery which has been used in previous trials in individuals with DS ^{48, 49} including our pilot trial ⁵⁰. The tests in this battery, which include

measures of multitasking, episodic memory, executive function, working memory, and processing speed, have demonstrated sensitivity to disease-specific cognitive deficits in DS, including those related to hippocampal dysfunction and frontal lobe dysfunction⁵¹ and are also sensitive to the changes in cognitive function seen in AD^{52, 53}. Detailed descriptions of these test are available at the CANTAB® website (<http://www.cambridgecognition.com>). All tests will be administered in a quiet room on an iPad in a following manufacturer's instructions. Tests will be administered in a random order and scored by [name] who will be blinded to intervention group. Based on results from our pilot trial, we expect completion of this battery will require ~30 min. We considered the use of the National Institutes of Health Toolbox Cognitive Battery; however, the psychometric properties for use of this battery in adults with DS are unacceptable⁵⁴.

Cardiovascular fitness. In adults without DS, cardiorespiratory fitness is associated with brain volumes in the medial, temporal, and parietal cortices, suggesting that increasing cardiorespiratory fitness, by increased MVPA, may modify AD-related brain atrophy^{55, 56}. A maximal treadmill test which are commonly used in adults with DS⁵⁷⁻⁵⁹, will be completed at baseline, 6, and 12 mos. Heart rate (Polar RS 400) and expired O₂ and CO₂ (ParvoMedics TrueOne 2300 - calibrated prior to each test) will be measured in 20 second intervals. We will follow the protocol by Fernal et al for individuals with and without ID⁶⁰. The protocol starts with a 2-min warm-up at a comfortable walking speed. After the warm-up, the speed will be adjusted to a brisk walking speed. After 2 min of walking at a brisk speed and 0% grade, the grade will increase every 2 mins by 2.5% until a 12.5% grade is reached. From that point on, grade will be held constant, whereas speed will be increased by 1.6 or 0.8 km·h⁻¹ every minute until exhaustion. The test will be ended when the participant hits two or more of the following four criteria of peak effort: 1) test ended because of volitional exhaustion, 2) VO₂ or HR plateau with an increase in work rate (VO₂ plateau defined as an increase less than 150 mL·min⁻¹; HR plateau defined as an increase less than 2 bpm), 3) HRpeak within 5 beats of predicted HRpeak according to the formulas of Fernhall et al.⁶⁰, and 4) an RER >1.10. The exercise test will be terminated early if the participant can no longer keep up with the treadmill speed or ask to stop. A cardiologist will be on-site for all treadmill tests per American College of Sports Medicine recommendations for testing individuals with DS⁶¹.

Quality of Life. Quality of life will be assessed at baseline, 6, and 12 mos. with the Personal Well-Being Index-Intellectual Disability(PWI-ID)^{62, 63}. This instrument contains 7 items, each corresponding to a quality of life domain: standard of living, health, life achievement, personal relationships, personal safety, community-connectedness, and future security. Cronbach alpha of 0.76, and 1- to 2-wk. test-retest reliability of 0.58 have been reported in adults with IDD⁶². The PWI-ID scale differs from the original Personal Well-Being Index (PWI-A) in that it incorporates a pre-testing protocol to determine whether, and to what level of complexity, respondents are able to use the scale. The ID version also uses more simple and concrete wording. An additional question which asks how happy or sad the respondent is with life as a whole is included. A reduced choice format, illustrated as a series of outline faces, from very sad to happy, is provided to enhance comprehension and substitutes for the Likert scale used in the PWI-A version⁶³.

Neuroimaging (Sub-sample).. Neuroimaging measures of brain volume i.e. structural MRI, functional connectivity, i.e. resting state MRI (rsMRI), blood flow, i.e. arterial spin labeling (ASL), and spectroscopy (MRS) will be assessed at baseline, 6, and 12 mos. utilizing the scan parameters currently implemented by the NIAD and ABC-DS Structural MRI imaging has elucidated the specific brain regions impacted by dementia in DS. These grey matter changes are detectable prior to the development of signs of clinical dementia^{64, 65} and have been impacted by cardiovascular fitness/MVPA⁵⁶. Structural MRI is a feasible test in adults with DS. In a recent review of 9 trials that used rsMRI in adults with DS⁶⁶, 4 reported no scanning issues, and in the remaining 5, ~17% of participants were excluded due to motion artifact with those who have more severe intellectual

disabilities being more likely to move during the scan. However, only individuals with mild to moderate intellectual disabilities will be included in this study, which will decrease the likelihood of motion during the scan. To further reduce motion during the scan and to minimize attrition, participants will have the option to partake in a practice session before the scheduled baseline scan. For the practice session, participants will be introduced to Hoglund study team members, lie in the scanner with the appropriate head coil while 3 minutes of a study sequence runs. The practice session will last ~15 minutes and a safety screener will be completed at the beginning of the practice session. Volumetric analyses of overall and regional, e.g. hippocampus, brain volumes will be performed using FreeSurfer segmentation using the longitudinal processing stream ⁶⁷, which is currently being implemented for the Alzheimer's Disease Center registry data at KUMC. rsMRI examines functional connectivity within and between brain networks. Individuals with DS show increased connectivity between networks compared to typically developing adults which has been hypothesized to reflect increased compensatory brain activation ⁶⁸. Pre-processing of rsMRI data will be performed for each participant using Analysis of Functional NeuroImages (AFNI, Medical College of Wisconsin). The rsMRI images will be realigned to the first slice collected in each scanning session to correct for motion. The images will be spatially smoothed with a 4 mm Full Width Half Maximum (FWHM) Gaussian blur. Functional and anatomic images obtained in each session will be aligned and normalized to a DS brain template ⁶⁸. An ASL sequence will be collected to measure changes in blood flow that may be related to increased fitness associated with physical activity. ASL analyses will be performed using the ASL Toolbox ⁶⁹ with Statistical Parametric Mapping version 12 software (SPM12) ⁷⁰ and applying methods that are currently implemented for the Alzheimer's Disease Center registry at KUMC.

Energy expenditure of Exercise Sessions (Sub-sample).. Energy expenditure of the remote sessions will be assessed in a volunteer sample using a previously validated portable, open-circuit indirect calorimeter (Pnoe, Greece) which measures breath-by-breath ventilation, expired oxygen, and carbon dioxide. The flow turbine will be calibrated using a 3.0-L syringe. The lightweight (~1.5 kg) portable system will be attached by a harness around the waist and shoulders of the participant before each assessment. During exercise sessions, participants will breathe into a facemask that directs air into the unit housing the O₂ and CO₂ analyzers. Data will be retrieved for analysis via a serial port interface and software provided with the calorimeter, and aggregated over 20-second epochs for the calculation of 1-min averages. MET levels will be age corrected using the Schofield equation ⁷¹ as recommended by McMurray et al ⁷².

Physical Function (Sub-sample). Functional lower extremity strength will be assessed using the Five Times Sit to Stand test (5XSTS)^{73, 74}. Participants are asked to sit with arms folded across their chest and with their back against a free-standing chair. They are instructed to stand up and sit down five times in a row as quickly as they can. The score is the amount of time it takes to complete the task (seconds). Functional mobility will be assessed using the Timed Up and Go (TUG) test ^{69,70}. From a sitting position in a standard arm chair participants are asked to stand up, walk to a line 10 feet away, turn around, return to the chair and sit down. The score is the time (seconds) it takes to complete the task. Grip strength for both the dominant and non-dominant hands will be assessed using a Jamar hand grip dynamometer (JWL Instruments, Chicago, IL). Participants are asked to hold their arm with their elbow bent at a 90-degree angle and to squeeze the dynamometer as hard as possible using a smooth motion. The procedure is repeated three times with the average of the three readings used in the analysis. I/ADL will be assessed using the 17-item Waisman Activities of Daily Living survey (W-ADL)⁷⁵.

Caregiver Outcomes (Sub-sample).. Caregiver burden will be assessed using the Center for Epidemiological Studies Depression Scale (CES-D)⁷⁶ which captures multiple aspects of caregiver

burden (physical, emotional, financial). Caregiver stress will be assessed using the Caregiver Self-Assessment Questionnaire (CSAQ), which is a caregiving-specific measure of psychosocial stress and is an appropriate measure for depression screening⁷⁷. Caregiver quality of life will be assessed using the Adult Carer Quality of Life Questionnaire (AC-QoL)⁷⁸, which covers eight different domains for caregivers: support for caring; caring choice; caring stress; money matters; personal growth; sense of value; ability to care; and caregiver satisfaction.

Feasibility. Retention. Retention will be measured as the percentage of participants who complete the 12 mo. intervention, defined as completing the 12 mo. outcome assessments. Session attendance. Session attendance for both group MVPA and individual education/support sessions from baseline to 12 mos. will be obtained from records maintained by the health educator, and expressed as the percent of possible sessions. Attendance at group MVPA sessions will be defined as being logged in to the video conference and remaining on the screen for the entire 30-min session. Attendance at individual support/education sessions, for the both exercise and UC conditions, will be defined as answering the Zoom call, and being present on screen for the entire session. Use of recorded exercise sessions (RL and RH only) will be tracked using Dropbox which provides information on how many times each user watched a video. Safety. Safety will be measured by number of participants reporting a serious adverse event, i.e., any untoward medical occurrence that results in death, is life-threatening, requires inpatient hospitalization or results in persistent or significant disability/incapacity.

Descriptive outcomes. To characterize our study sample, we will measure weight, height and waist circumference in participants at baseline, 6, and 12 mos. Weight will be measured in light clothing on a calibrated scale (Model #PS6600, Belfour, Saukville, WI) to the nearest 0.1 kg. Standing height will be measured with a portable stadiometer (Model #IP0955, Invicta Plastics Limited, Leicester, UK). BMI will be calculated as weight (kg)/height (m²). Waist circumference will be assessed using the procedures described by Lohman et al.⁷⁹.

Exit interview. At the end of the intervention, [name] will conduct structured interviews by phone with a 20% random sample of participants and study partners from each intervention arm to gather information that might be useful for improving the intervention. Topics will include preference for the RH, RL, or UC arms, reasons for missing scheduled sessions, intervention length, difficulties with compliance, suggestions for improvements and overall satisfaction with the intervention, enjoyment of the MVPA and educational sessions, health educators, MVPA recommendations, satisfaction with the MRI scan protocol, and willingness to take part in outcome procedures that could be used in future studies (collection of spinal fluid, PET scan). Additionally, we will interview all caregivers to explore caregiver perspectives on the role and potential impact of increased MVPA for healthy aging in adults with DS and how improved physical function in adults with DS in their care may impact their caregiving

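### The treadmill protocol uses the four peak-effort criteria as a rule for ending the test, so read literally it can stop a maximal test before exhaustion

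*Combined protocol and SAP*

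**What the plan says.** The Cardiovascular fitness paragraph under Assessments in section 5 describes the measure as "A maximal treadmill test which are commonly used in adults with DS", done at baseline, 6 and 12 months. After the grade reaches its ceiling, speed goes up "every minute until exhaustion".

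The next sentence gives the rule at issue: "The test will be ended when the participant hits two or more of the following four criteria of peak effort". The criteria are:

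1. "test ended because of volitional exhaustion";
2. a plateau in VO2 or in heart rate as work rate increases, with the VO2 version set at a rise under 150 mL/min and the heart-rate version given as "HR plateau defined as an increase less than 2 bpm";
3. "HRpeak within 5 beats of predicted HRpeak according to the formulas" of a cited source;
4. RER above 1.10.

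The paragraph adds: "The exercise test will be terminated early if the participant can no longer keep up with the treadmill speed or ask to stop".

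Heart rate and expired gases are recorded in 20-second intervals. Section 8.3 correlates change in MVPA with change in cardiovascular fitness at 6 and 12 months, pooled over arms. No other section restates the four criteria as a check on a completed test, and section 8.3 does not say how a test meeting none or one of them is handled.

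**The concern.** Two consecutive sentences give different end points. One runs the participant to exhaustion. The other ends the test once two listed signs are present, and three of those signs can appear while the participant is still able to go on. The remaining sign is that the test is over, which makes the rule circular on that item.

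This treadmill test is the only fitness assessment described, so its stopping rule decides what the outcome measures. A tester who follows the rule literally may record a value below the participant's peak. A tester who follows the sentence before it will not. If practice differs between visits or testers, the difference enters the change score that section 8.3 correlates with change in MVPA.

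**Working it through.** The plan gives no figure to reproduce here, so the check is one of logic.

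**Step 1: count the ways to meet the rule.** With four criteria, the combinations of two or more number 6 (pairs) + 4 (triples) + 1 (all four) = 11.

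**Step 2: remove those that cannot stop a running test.** Criterion 1 is true only once the test is over. The combinations that contain it pair it with one, two or three of the other criteria: 3 + 3 + 1 = 7. None of these can be the trigger. That leaves 11 − 7 = 4.

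**Step 3: look at the four that can act as triggers.**

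| Combination | What has been observed | Likely consequence of stopping |
|---|---|---|
| 2 + 3 | plateau; heart rate near predicted | depends on which plateau |
| 2 + 4 | plateau; RER above 1.10 | depends on which plateau |
| 2 + 3 + 4 | all three | depends on which plateau |
| 3 + 4 | heart rate near predicted; RER above 1.10 | no plateau of any kind is required, so VO2 may still be rising |

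Three of the four contain the plateau criterion. If VO2 itself has levelled off despite more work, ending the test should lose little. If criterion 2 was met only through heart rate, nothing in the rule shows that VO2 has stopped rising. The exposed cases are therefore 3 + 4 without a VO2 plateau, and the plateau combinations in which the plateau is in heart rate only.

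**Step 4: compare with the neighbouring sentences.** In those exposed cases the instruction to continue until exhaustion and the instruction to end the test cannot both be followed. The early-termination sentence does not conflict in the same way. It lets a participant who cannot keep up or wants to stop do so, and it only overlaps with exhaustion. The overlap does leave a gap in classification. The same observed act could be logged as volitional exhaustion, which counts towards peak effort, or as a request to stop, which is called early termination. The text gives no way to tell them apart.

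**Step 5: size.** The documents give no VO2 values, no stage-by-stage gain, no expected training effect and no frequency for any of the combinations. They do not name the fitness variable to be analysed either. No estimate of the bias follows from them.

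**The case against.** The strongest reply is that this is a slip in one verb. The test is called maximal, the items are called criteria of peak effort, criterion 1 is in the past tense, and criterion 3 refers to a peak heart rate, strictly known only afterwards. The test also follows a cited published protocol that may settle termination, and section 5 says trained staff do the assessments. On this view staff run to exhaustion and apply the list afterwards.

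Much of that stands. It is probably what was meant, and the list makes best sense as a check on a completed test. It does not remove the point. The sentence is an operating instruction, nothing else in the plan corrects it, and a tester can compare current heart rate with the predicted value during the test. The cited source is not available here, so it can neither rescue nor condemn the wording.

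A second reply is that a rule read the same way at every visit would largely cancel in a change score, and that uneven reading would mainly add noise. That also stands, and it limits the harm. Blinding does not decide the matter: section 5 says assessors are blinded, while section 8.1.1 says the study team is not.

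Stronger readings are tempting. A reader might infer that fitness will be understated in general, by as much as a training effect. The documents give neither quantity, and stopping at a true VO2 plateau should cost little. A reader might also infer bias between arms. Nothing in the plan supplies a mechanism by which the rule would be applied differently by arm.

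**Conclusion.** The point holds as a minor correction to a secondary outcome. The peak-effort criteria are worded as a stopping rule, which conflicts with running the test to exhaustion and is circular for criterion 1. Followed literally, the rule permits stopping before peak, mainly when heart rate is near predicted and RER exceeds 1.10 without a VO2 plateau, or when the plateau criterion rests on heart rate only. The result could be an understated or inconsistent fitness value, by an amount that the documents do not let one estimate.

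This rests on two assumptions: that at least some testers would act on the sentence as written, and that the fitness variable is a peak value from this test. The plan confirms neither.

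**What to change.** Replace the stopping sentence and merge it with the early-termination sentence, along these lines: *The test continues to volitional exhaustion, or until the participant cannot keep up, asks to stop, or is stopped for safety; the reason for stopping is recorded. A completed test is classed as peak effort if two or more of the four criteria are met.*

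In section 8.3, state that all tests are analysed, and that the correlation of change in fitness with change in MVPA is repeated, as a sensitivity analysis, in tests classed as peak effort. Because the outcome is a change, both the baseline and the follow-up test need that class.

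The cost is small: a wording change, one recorded reason for stopping, and one derived flag. Criteria 2 to 4 use data already collected every 20 seconds. The downside is fewer tests in the sensitivity analysis. Section 8.3 already puts the detectable correlation at 0.36 in absolute value with 60 participants, and with fewer than 60 pairs of tests it would be larger, so that analysis should be read as a check on consistency.
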